10.1.2 Exploratory Endpoints

Stratum A:

 Induction of the H3.3K27M epitope-specific CTL response in post vaccine PBMCs in HLA-A2 (02:01)+ children with H3.3K27M positive gliomas other than DIPG
- Assessment of H3.3K27M infiltrates in subjects with evidence of progression that undergo tissue collection as part of their standard of care. Tumor tissue will be analyzed for H3.3K27M expression status and infiltration of H3.3K27M specific T cells
- To archive tumor and normal DNA from each subject at time of initial diagnosis along with serial blood draws following therapy to determine whether circulating tumor DNA (ctDNA) sequences in the subject's blood serve as biomarkers of tumor burden, response to therapy, or development of drug resistance.

Stratum B:

- Induction of the H3.3K27M epitope-specific CTL response in post vaccine PBMCs in HLA-A2 (02:01)+ children with H3.3K27M positive gliomas other than DIPG
- Assessment of H3.3K27M infiltrates in subjects with evidence of progression that undergo tissue collection as part of their standard of care. Tumor tissue will be analyzed for H3.3K27M expression status and infiltration of H3.3K27M specific T cells
- To archive tumor and normal DNA from each subject at time of initial diagnosis along with serial blood draws following therapy to determine whether circulating tumor DNA (ctDNA) sequences in the subject's blood serve as biomarkers of tumor burden, response to therapy, or development of drug resistance.

Stratum C:

- To determine the OS12 in HLA-A2 (02:01)⁺ children with H3.3K27 positive DIPGs and midline gliomas (excluding primary spinal cord tumors) that are treated with repeated administration of the H3.3K27M peptide and nivolumab.
- Induction of the H3.3K27M epitope-specific CTL response in post vaccine PBMCs in HLA-A2 (02:01)+ children with H3.3K27M positive gliomas including DIPG or other H3.3K27M positive midline gliomas, excluding primary spinal cord tumors.
- To archive tumor and normal DNA from each subject at time of initial diagnosis along with serial blood draws following therapy to determine whether circulating tumor DNA (ctDNA) sequences in the subject's blood serve as biomarkers of tumor burden, response to therapy, or development of drug resistance.
- To assess Quality of Life (QoL) and cognitive measures in HLA-A2 (02:01)⁺ children with H3.3K27M positive DIPG or other midline gliomas.

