With a null hypothesis that OS12 is 40%, a sample size of 19 patients achieves 80% power to detect a difference of 30% using a one sided exact binominal test⁴⁰. The target significance level is 5% and the actual significance level is 3.5% with this test. If 12 or more patients are alive at 12 months, the null hypothesis that OS12 is 40% will be rejected. Patients lost to follow-up before 12 months will be considered events. OS12 will be estimated from the Kaplan-Meier method. Two-sided 95% CI will be computed based on the Greenwood's formula. If the null hypothesis is truly OS12 = 30% or OS12 = 50%, a sample size of 19 patients still achieves 80% power to detect a difference of 30%, however, the number of patients needed to reject the null changes to n = 10 or n = 14, respectively.

For the secondary endpoint for stratum C, we will assess the efficacy endpoint (OS12) in 20 evaluable patients with H3.3K27M positive DIPG or other midline gliomas, excluding primary spinal cord tumors.

In comparing outcomes to other H3K27M positive midline gliomas, OS rates similar to those for Stratum A are reported, although the reference literature is sparser for this patient population^{31,32}. Thus, similar to stratum A, a sample size of 20 patients achieves 80% power to detect a difference of 30% using a one sided exact binominal test (see above)⁴⁰.

At time of data analysis, we will use the most recent published data and PNOC enrollment data in order to determine the appropriate null rate for stratum A and stratum C.

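### Stratum C OS12: 20 patients give 77% power, not the stated 80%, at the 40% planning null, and no cut-off for 20 patients is printed

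*Combined protocol and SAP*

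**What the plan says.** Section 10.2.1 sets out the Stratum A design in full: 19 patients, a null OS12 of 40%, a 30-point improvement, a one-sided exact binomial test, and rejection if 12 or more are alive at 12 months. On the level it says: "The target significance level is 5% and the actual significance level is 3.5% with this test". For nulls of 30% and 50% it still claims 80% power and adds that "the number of patients needed to reject the null changes to n = 10 or n = 14, respectively".

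For Stratum C the same section says "For the secondary endpoint for stratum C, we will assess the efficacy endpoint (OS12) in 20 evaluable patients". It reports that survival in the other midline gliomas is similar to Stratum A, and concludes that "a sample size of 20 patients achieves 80% power to detect a difference of 30% using a one sided exact binominal test", with a pointer back to the text above. It prints no null, cut-off or actual level for 20 patients.

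The section closes by saying that the latest published data and consortium data will be used at analysis "in order to determine the appropriate null rate for stratum A and stratum C".

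Sections 2.2 and 10.1.2 list Stratum C OS12 among the exploratory items ("To determine the OS12 in HLA-A2"), while 10.2.1 calls it secondary.

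**The concern.** The power of an exact binomial test does not rise steadily with sample size, because the cut-off moves in whole patients. A figure that is right for 19 patients cannot be assumed for 20. The Stratum C sentence reads as if the Stratum A result had been carried over without being recalculated.

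Two things are at stake. The stated power may be untrue at the null on which the calculation rests. And a reader who follows the pointer back finds only cut-offs for 19 patients, some of which may not hold the 5% level in 20. For Stratum A, each named null at least comes with a printed cut-off; for Stratum C none does.

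**Working it through.** **Inputs, all from section 10.2.1.** n = 19 (Stratum A) and n = 20 (Stratum C); null p0 = 40%, with 30% and 50% as the other named values; alternative p1 = p0 + 30 points; one-sided exact binomial test; target level 5%. Patients lost before 12 months count as deaths, so every patient contributes a yes/no result.

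**Formulas.** With X the number alive at 12 months:
- cut-off c = the smallest c with P(X ≥ c | n, p0) ≤ 0.05
- actual level = P(X ≥ c | n, p0)
- power = P(X ≥ c | n, p0 + 0.30)

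**Step 1: reproduce Stratum A (n = 19).**

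| Null | Cut-off | Actual level | Power |
|---|---|---|---|
| 30% | 10 | 3.3% | 81.4% |
| 40% | 12 | 3.5% | 81.8% |
| 50% | 14 | 3.2% | 83.7% |

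The cut-offs, the 3.5% level and the claim of 80% power all match the plan, so this is the plan's own method.

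**Step 2: the same method for Stratum C (n = 20).**

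| Null | Cut-off | Actual level | Power |
|---|---|---|---|
| 30% | 10 | 4.80% | 87.2% |
| 40% | 13 | 2.10% | 77.2% |
| 50% | 15 | 2.07% | 80.4% |

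At the 40% null, a cut-off of 12 would give 88.7% power, but P(X ≥ 12 | 20, 0.40) = 5.65%, which exceeds the target. The cut-off must therefore be 13, and P(X ≥ 13 | 20, 0.70) = 77.2%. The shortfall is 80.0 − 77.2 = 2.8 points. With cut-off 13, a true rate of 71% gives 80.2% power.

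**Step 3: neighbouring sizes at 40% against 70%.** n = 19 gives 81.8% (cut-off 12), n = 20 gives 77.2% (cut-off 13) and n = 21 gives 85.2% (cut-off 13, level 3.5%). The dip comes from the cut-off moving from 12 to 13 between 19 and 20 patients.

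**Step 4: the printed cut-offs if applied to 20 patients.** P(X ≥ 10 | 0.30) = 4.80%, P(X ≥ 12 | 0.40) = 5.65% and P(X ≥ 14 | 0.50) = 5.77%. Only the first stays within 5%.

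**Step 5: could another convention explain 80%?** At n = 20 and 40% against 70%, a two-sided exact test also gives 77.2%. A mid-p rule, or a 10% level, moves the cut-off to 12 and gives 88.7%. One-sided normal approximations give 87.9%, or 82.3% with continuity correction. A two-sided 5% normal approximation without correction gives 79.7%, but it is not the test the plan names.

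**The case against.** The Stratum C sentence prints no null, and the plan defers the choice to analysis. The consortium figure it quotes is 50%, where 20 patients do give 80.4%; at 30% they give 87.2%. So the claim holds at two of the three named nulls. The shortfall is also an accident of the exact value: a null of 39% gives 86.6% (cut-off 12) and 41% gives 80.2% (cut-off 13). Over whole-percent nulls from 30% to 50%, power is at least 80% at 16 of 21 values and never below 76%. Once a null is fixed, the named test and the 5% target determine the cut-off, so an unprinted cut-off is a gap in presentation. Finally, the endpoint is not primary, and under section 10.3.1 all enrolled patients enter the efficacy analysis, so the number analysed may exceed 20.

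Most of this stands as a limit on importance. The 40% null is inherited rather than restated, nothing says the cut-offs for 19 patients will be reused, and the sample size need not change. It does not make the sentence true. Section 10.2.1 ties Stratum C to Stratum A by similar survival, by direct analogy and by a pointer back, and the planning null found there is 40%. For Stratum A the plan claims 80% at all three nulls; for Stratum C that cannot be claimed.

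**Conclusion.** The stated 80% is wrong at the 40% planning null: the specified test has 77.2% power with 20 patients, at a cut-off of 13 and an actual level of 2.1%. It is right at nulls of 30% and 50%. No cut-off is printed for 20 patients at any null, and two of the three printed for 19 would exceed 5% if used in 20.

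This rests on reading the 40% null and 5% one-sided target as carried over from Stratum A, and on exactly 20 patients being analysed. The consequence is modest: a 2.8-point overstatement on a non-primary endpoint, with Stratum C's safety objective and the Stratum A calculation unaffected. It should still be corrected, because the rule ought to be written down before outcomes are known. The exploratory/secondary mismatch is editorial and adds no weight.

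**What to change.** Replace the Stratum C power sentence in 10.2.1 with:

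*Stratum C, n = 20, one-sided exact binomial test, 5% target level. Null 30%: reject if 10 or more are alive at 12 months (actual level 4.8%, power 87% at 60%). Null 40%: 13 or more (2.1%, 77% at 70%). Null 50%: 15 or more (2.1%, 80% at 80%). The Stratum A cut-offs for 19 patients do not apply.*

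Because the null or the number analysed may turn out different, add that in that case the cut-off is the smallest count whose exact one-sided level does not exceed 5%.

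Use one label, exploratory or secondary, for Stratum C OS12 in 2.2, 10.1.2 and 10.2.1.

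The cost is one sentence replaced, one short clause added and one label aligned. No patients are added and the design does not change; the stated power at the 40% null becomes about 3 points less favourable.

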If enrollment commences, all additional patients will be monitored continuously for treatment-related adverse events by the study PIs Drs. [name] and [name]. With six patients, there is an 88% probability of detecting 1 or more RLTs with an underlying rate of 30%. There is a 74% probability of detecting 1 or more RLTs with an underlying rate of 20%. If all 19 patients are enrolled in Stratum A, there is an 86% probability of detecting 1 or more RLTs with an underlying rate of 10% and a 62% probability with an underlying rate of 5%. If all 10 patients are enrolled in Strata B, there is a 65% probability of detecting 1 or more RLTs with an underlying rate of 10% and a 40% probability with an underlying rate of 5%. If all 20 patients are enrolled in Strata C, there is an 88% probability of detecting 1 or more RLTs with an underlying rate of 10% and a 64% probability with an underlying rate of 5%.

Enrollment into Stratum C will start once Strata A and B have completed accrual.

- **10.2** Determination of Sample Size and Accrual Rate
- **10.2.1** Sample Size and Power Estimate

For the primary endpoint for stratum A, we will assess the efficacy endpoint (OS12) in 19 evaluable patients with H3.3K27M positive DIPG. Prior research has shown overall survival for children with DIPG ranges from 30-40% at 12 months^{38,39}. The most recent Children's Oncology Group study that treated children newly diagnosed with DIPG with a combination of radiation therapy and temozolomide resulted

in an OS12 rate of 40% (SD \pm 6.5%)¹. Review of outcomes of DIPG patients on PNOC studies of children and young adults with newly diagnosed DIPG who received standard of care radiation therapy revealed an OS12 rate of 50% (PNOC003 - NCT02274987 and PNOC007 - NCT02960230, unpublished data). For PNOC003 patients were enrolled prior to the start of radiation therapy - similar to the COG study- and none of the enrolled patients came off study due to progression during or at completion of radiation therapy making this a reasonable control group for this study.

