10.2.2 Accrual estimates

This study aims to enroll 19 children with H3.3K27M positive DIPG (Stratum A), 10 children with H3.3K27M positive glioma, other than DIPG, including spinal cord tumors (Stratum B) and 20 children with H3.3K27M positive DIPG or other midline gliomas, excluding primary spinal cord tumors (Stratum C). Eligible patients need to test positive for the HLA-A02:01⁺ to be eligible. Based on our previous study, we anticipate that about 40 children with DIPG and 40 children with other gliomas will need to be screened to meet accrual goals¹⁴. We anticipate that most of the PNOC sites will open this study and that we will be able to screen 2-3 potentially eligible patients per month which would allow us to accrue at least one patient per month. To date, we have enrolled an average of 1.4 patients/month on the phase 1 portion of PNOC007 with 14 PNOC sites actively accruing. To date, enrollment has been similar between the strata. Therefore, we anticipate that enrollment onto Strata A and B will be completed in approximately two years. We anticipate that Stratum C will follow a similar pattern, taking up to 2 years for enrollment.

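### The Stratum A OS12 null is printed as 40% but left to be set at data analysis with no rule keeping it independent of the outcomes, so 10 to 13 alive of 19 has no settled verdict

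*Combined protocol and SAP*

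**What the plan says.** Section 10.2.1 of the combined protocol and SAP specifies a one-sided exact binomial test for Stratum A with 19 patients, a 40% null and a 30-point improvement. The target level is 5%, the actual level 3.5% and the power 80%. The decision rule is explicit: "If 12 or more patients are alive at 12 months, the null hypothesis that OS12 is 40% will be rejected". If the true null is 30% or 50%, "the number of patients needed to reject the null changes to n = 10 or n = 14, respectively".

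The section then ends: "At time of data analysis, we will use the most recent published data and PNOC enrollment data in order to determine the appropriate null". This provision applies to both Stratum A and Stratum C. For Stratum C it says that, "similar to stratum A, a sample size of 20 patients achieves 80% power to detect a difference of 30" percentage points.

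Three reference rates are cited there: a 30-40% range from prior research; a cooperative-group trial that resulted "in an OS12 rate of 40" per cent (SD 6.5%); and a review of DIPG patients on PNOC studies that "revealed an OS12 rate of 50% (PNOC003 - NCT02274987 and PNOC007 - NCT02960230, unpublished data". Section 10.2.2 shows that PNOC007 is this trial: "we have enrolled an average of 1.4 patients/month on the phase 1 portion of PNOC007". The argument that the comparison group is reasonable is made for PNOC003 only.

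Section 10.3.2 makes OS12 the primary efficacy endpoint of Stratum A and plans a Kaplan-Meier estimate with a Greenwood interval. It names no null and no cut-off.

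**The concern.** A single-arm test has its stated error rate only when the null is fixed without reference to the data being tested. Here the null is to be picked at analysis from two broad classes of source, and nothing says who picks it, from what, as of when, or without sight of OS12.

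Two features make this more than a formality. First, one of the two source classes can include the tested patients themselves, because the 50% PNOC rate draws on PNOC007. Second, Stratum A's 12-month status was already determinable some time ago. Section 5.1.5 has all 19 Stratum A patients treated by 12/31/18, Section 9.3.1.4 counts survival from diagnosis, and Section 1.3 reports a cut-off of September 8, 2020.

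At stake is whether the Stratum A primary efficacy result is called a success.

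**Working it through.** **Inputs** (Section 10.2.1): n = 19; printed nulls 30%, 40%, 50%; cut-offs 10, 12, 14; 30-point gain; one-sided target 5%; losses before 12 months counted as events.

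**Formula.** P(X ≥ k | n, p) = Σ from x = k to n of C(n, x) pˣ (1 − p)ⁿ⁻ˣ. The cut-off is the smallest k for which this is at most 0.05 at the null. Power is the same tail at the null plus 0.30.

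**1. The plan's own figures reproduce.**

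| Null | Cut-off | Alpha | Power at +30 points |
|---|---|---|---|
| 30% | 10 | 3.3% | 81.4% |
| 40% | 12 | 3.5% | 81.8% |
| 50% | 14 | 3.2% | 83.7% |

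Each row is a valid test if its null is fixed independently of the results. The gap is that no rule selects the row.

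**2. Which results are open.** One-sided exact p-values at n = 19:

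| Alive | Null 30% | Null 40% | Null 50% |
|---|---|---|---|
| 10 | 0.0326 | 0.1861 | 0.5000 |
| 11 | 0.0105 | 0.0885 | 0.3238 |
| 12 | 0.0028 | 0.0352 | 0.1796 |
| 13 | 0.0006 | 0.0116 | 0.0835 |
| 14 | 0.0001 | 0.0031 | 0.0318 |

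At 9 or fewer alive no printed null is rejected, and at 14 or more all three are. From 10 to 13 the verdict depends on the null. Between 40% and 50% alone, the open results are 12 and 13.

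**3. How likely an open result is.**
- 10 to 13 alive: at a true 40%, 0.1861 − 0.0031 = 0.1830, or 18.3%; at a true 70%, 49.4%.
- 12 or 13 alive: 3.2% at a true 40%, 14.8% at 50%, 34.4% at 70%.

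**4. Effect on error.** If the true rate is 40% and the 30% null is adopted, success needs only 10 alive: P(X ≥ 10 | 19, 0.4) = 18.6%, against the stated 3.5%. Moving from 40% to 50% works the other way: P(X ≥ 14 | 19, 0.4) = 0.3%.

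**5. Updates between the printed nulls.** At the 5% level, 12 is the cut-off only for nulls from 36.8% to 41.8%. It is 13 up to 47.0%, and 14 above that. An update from 40% to 42% would therefore reverse the verdict at 12 alive.

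**6. Timing.** From 12/31/18 to September 8, 2020 is 365 + 252 = 617 days. With survival counted from diagnosis, every Stratum A patient had passed 12 months by then.

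**7. Stratum C, n = 20, same method.**

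| Null | Cut-off | Alpha | Power at +30 points |
|---|---|---|---|
| 30% | 10 | 4.8% | 87.2% |
| 40% | 13 | 2.1% | 77.2% |
| 50% | 15 | 2.1% | 80.4% |

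At a 40% null, 12 or more gives alpha 5.65%, above the target, so the stated 80% is not reached at that null.

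**The case against.** The strongest defence is that updating a historical rate is sensible when care changes, and that all three cut-offs are printed so a reader can apply each. The updating argument has force. If the true background is 50%, the 40% rule succeeds 18.0% of the time, and that is a cost of *not* updating. A reader might take the 18.0% as the harm done by choosing late, but it is not. The inflation attributable to the open choice is the 18.6% under the 30% null. If only 40% and 50% were in play, error at a true 40% would stay at or below 3.5%.

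A reader might also infer that the 40% rule was written, or will be replaced, with the outcomes in view. The documents do not show this. They show that 12-month status had matured by September 2020. They do not show when the rule was first set, and it may predate enrolment. Nor do they give the share of PNOC007 patients in the 50%.

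The consequence is also limited. The Kaplan-Meier estimate and its interval do not involve the null, and no accrual decision depends on rejection: "Enrollment into Stratum C will start once Strata A and B have completed accrual". The sensitivity to a 2-point shift partly reflects discreteness at n = 19, and no single cited rate lies between 40% and 50%.

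What remains is that printing three valid tests does not supply a rule for choosing among them, and one candidate null draws on the trial under test.

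**Conclusion.** The point stands and should be fixed. As written, the null for the Stratum A primary efficacy test could depend on the outcomes, so the stated 3.5% is not guaranteed. Results from 10 to 13 alive are open across the printed nulls, and 12 or 13 between 40% and 50% alone. The design arithmetic for Stratum A is correct. The Stratum C power statement fails at the 40% null by just under 3 points (77.2% against 80%). OS12 is exploratory there according to Sections 2.2 and 10.1.2, although Section 10.2.1 calls it secondary.

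The figures assume independent patients, exactly 19 or 20 analysed, and the smallest cut-off with one-sided alpha at most 5%. The documents support a finding of a missing safeguard. They do not support a finding that the null was or will be chosen to suit the result, or that the survival estimate itself is compromised.

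**What to change.** **Stratum A.** Delete the last sentence of Section 10.2.1 and keep the printed 40% null with 12 or more of 19 as the single decision rule. State in the report when that null was fixed relative to the maturing of OS12. Show results against 30% (cut-off 10) and 50% (cut-off 14) as labelled sensitivity analyses only. Note there that the 40% rule gives 18.0% success if the true background rate is 50%, and that the 50% includes this trial's own patients unless it is recomputed from PNOC003 alone.

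**Stratum C.** Before its outcomes are reviewed, fix one null and one cut-off from sources that exclude PNOC007, and restate the power from the table in step 7.

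**Cost.** Wording and a few reporting lines, with no new data or patients. The sponsor gives up the freedom to update the Stratum A null, and the stated Stratum C power becomes slightly less favourable if 40% is the null chosen.

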10.2.2 Accrual estimates

This study aims to enroll 19 children with H3.3K27M positive DIPG (Stratum A), 10 children with H3.3K27M positive glioma, other than DIPG, including spinal cord tumors (Stratum B) and 20 children with H3.3K27M positive DIPG or other midline gliomas, excluding primary spinal cord tumors (Stratum C). Eligible patients need to test positive for the HLA-A02:01⁺ to be eligible. Based on our previous study, we anticipate that about 40 children with DIPG and 40 children with other gliomas will need to be screened to meet accrual goals¹⁴. We anticipate that most of the PNOC sites will open this study and that we will be able to screen 2-3 potentially eligible patients per month which would allow us to accrue at least one patient per month. To date, we have enrolled an average of 1.4 patients/month on the phase 1 portion of PNOC007 with 14 PNOC sites actively accruing. To date, enrollment has been similar between the strata. Therefore, we anticipate that enrollment onto Strata A and B will be completed in approximately two years. We anticipate that Stratum C will follow a similar pattern, taking up to 2 years for enrollment.

10.3 Interim Analyses and Stopping Rules

The study will be monitored by Drs. [name] and [name] and the PNOC Operation's office on a weekly basis including a review of all adverse events and deviations entered within Advarra[®] in concordance with the PNOC requirements for phase 1/2 clinical trials. The toxicity monitoring rules for the following events will be applied to all patients treated in the study. The regimen limiting toxicity (RLT) will be based on the tolerability observed following the vaccine doses following radiation therapy.

RLT includes any of the following events that occur during or following any vaccine given.

- Any grade 2 or greater autoimmune reaction.
- Any grade 3 or greater hematologic or non-hematologic toxicity with the exception of lymphopenia.
- Any life-threatening event.
- Any other unexpected Grade 2 or greater neurological deficit, which is possibly, probably, or definitely related to the vaccine therapy that does not respond within 21 days trial of 0.3mg/kg day dexamethasone or equivalent (max 12mg/day) or Avastin or equivalent (10mg/kg every 2 weeks for a maximum of 3 doses)

In addition to the stopping rules specific to the design detailed above, all patients will be monitored continuously for treatment-related adverse events by the study PIs Drs. [name] and [name].

Sequential boundaries will be used to monitor the RLT rate. The accrual will be halted if excessive numbers of RLTs are seen, that is, if the number of RLTs is equal to or exceeds b_n out of *n* patients with full follow-up (see table below). This is a Pocock-type stopping boundary that yields the probability of crossing the boundary at most 0.0475 when the rate of RLT is equal to the acceptable rate of 0.20.

For example, in Stratum A, the trial will be stopped if the number of RLTs is equal to or exceeds b_n out of *n* patients with completed follow-up.

Number of Patients, n 1 2 3 4 5 6 7 8 9 10 11 12 13 14 15 16 17 18 19

Boundary, b_n - - 34445556 6 6 7 7 7 8 8 8 9

This boundary is equivalent to testing the null hypothesis, after each patient, that the event rate is equal to 0.2, using a one-sided level 0.021430 test.

θ	φ*	E[Y]	SD[Y]	E[N]	SD[N]	E[Y/N]	SD[Y/N]
0.20	0.0475	3.70	1.62	18.51	2.39	0.21	0.13
0.30	0.2248	5.08	1.55	16.92	4.44	0.34	0.18
0.40	0.5327	5.60	1.49	14.00	5.76	0.48	0.20
0.50	0.8151	5.30	1.54	10.59	5.62	0.60	0.20

Definitions:

Y = the number of events, random, between 0 and N N = the number of patients, random, between 1 and K

 φ^* = the actual probability of early stopping (hitting the boundary)

E[] denotes the expected value (mean) SD[] denotes the standard deviation

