3.5 Study Timeline

This study aims to enroll 19 HLA-A2 (02:01)⁺ children with H3.3K27M positive DIPG (Stratum A), 10 HLA-A2 (02:01)⁺ children with H3.3K27M positive midline gliomas other than DIPG, including spinal cord tumors (Stratum B) and 20 HLA-A2 (02:01)⁺ children with H3.3K27M positive DIPG or midline gliomas other than DIPG, excluding primary spinal cord tumors (Stratum C). H3.3K27M status needs to be confirmed in a CLIA or equivalent approved laboratory. Eligible patients with positive H3.3K27M need to also test positive for HLA A*02:01in a CLIA or equivalent approved laboratory.¹⁴ We will enroll into the 3 strata separately, and the first 3 patients in each stratum will be observed for RLTs for at least 6 weeks before the next set of patients are enrolled in that stratum. We will enroll subjects onto stratum C once we have met total accrual onto strata A and B. See Section 9.3 for further information.

Based on our accrual into this trial we anticipate to enroll an average of 1.8 subjects per month. We anticipate that enrollment for strata A, B, and C will be similar and therefore we anticipate that enrollment into the K27M glioma strata will be completed in about two years for each stratum.

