6.3 Regimen Limiting Toxicity (RLT)

Each patient receiving K27M/TT peptide vaccination and poly-ICLC or K27M/TT peptide vaccination and poly-ICLC in combination with nivolumab will be evaluable for safety. The safety parameters include all laboratory tests and hematological abnormalities, physical findings, and spontaneous reports of adverse events reported to the investigator by patients.

RLT includes any of the following events that occur during the first 8 vaccine doses (the entirety of the time from the 1st vaccine administration through the 8th vaccine administration) and up to 30 days after the 8th vaccine administration and are considered either possibly, probably, or definitely to the vaccine:

- Any grade 2 or greater autoimmune reaction.
- Any grade 3 or greater hematologic or non-hematologic toxicity with the exception of lymphopenia.
- Any life-threatening event.
- Any other unexpected Grade 2 or greater neurological deficit, which is possibly, probably, or definitely related to the vaccine therapy that does not respond within 21 days trial of 0.3mg/kg day dexamethasone or equivalent (max 12mg/day) or Avastin equivalent (10mg/kg every 2 weeks for a maximum of 3 doses)

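### The RLT boundary in Section 10.3 counts only patients with full follow-up, an undefined term, so RLTs inside the window enter late and the printed E[N] is not expected enrolment

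*Combined protocol and SAP*

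**What the plan says.** Section 10.3 sets a Pocock-type boundary. Accrual is halted if the number of RLTs is "equal to or exceeds b_n out of *n* patients with full follow-up". The stratum A example repeats the condition as "b_n out of *n* patients with completed follow-up". The boundary is described as a test after each patient, "using a one-sided level 0.021430 test", and it "yields the probability of crossing the boundary at most 0.0475" "when the rate of RLT is equal to the acceptable rate of 0.20". A table for 19 patients gives E[N] of 18.51, 16.92, 14.00 and 10.59 at RLT rates of 20, 30, 40 and 50%. It also gives φ*, defined as "the actual probability of early stopping (hitting the boundary"), of 0.0475, 0.2248, 0.5327 and 0.8151. N is defined only as the number of patients.

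Section 10.3 does not say how long full follow-up is. Section 6.3 ends the RLT window "up to 30 days after the 8th vaccine administration", and Section 6.1.2 puts the 8th dose at week 21. The RLT definition in 10.3 covers events during or after any vaccine dose and has no end point.

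Section 10.1.4 adds a lead-in. Accrual is held for at least 6 weeks after the first 3 patients, and for 12 weeks after 6 patients if one of the first 3 had an RLT. It is suspended for 2 or more RLTs in either group. No later pause is tied to the boundary.

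**The concern.** Accrual continues while patients pass through a window of about 25 weeks. Read literally, an RLT in an early treatment week does not count towards the boundary until that patient's window closes, months later. After the lead-in, no other rule in the plan has a numeric threshold.

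Two things are at stake in stratum C, where safety of the vaccine with nivolumab is the only primary objective. The boundary may be reached only when most of the stratum has already been enrolled. A safety committee may also take E[N] as the number of children expected to be treated before a halt, and φ* as the chance of halting before the stratum is full. With delayed outcomes, neither reading holds.

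**Working it through.** **Inputs.** Null rate 0.20, pointwise level 0.02143, b_n and the table: Section 10.3. Window: 21 × 7 + 30 = 177 days, or 25.3 weeks (6.1.2 and 6.3). Accrual per month: 20 in up to 24 months = 0.83 for stratum C (10.2.2); 1.4 observed so far (10.2.2); and "we anticipate to enroll an average of 1.8 subjects per month" (3.5). The 6-week hold after patient 3 is from 10.1.4.

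**1. Reproduce the plan's figures.** b_n is the smallest r with P(X ≥ r | n, 0.20) ≤ 0.02143. For example, n = 3 gives 0.2³ = 0.008 at r = 3; n = 6 gives 0.01696 at r = 4; n = 19 gives 0.00666 at r = 9. All 19 values match. With f_n(y) = (1 − p) f_{n−1}(y) + p f_{n−1}(y − 1), and stopping when y ≥ b_n, E[N] = Σ n·P(stop at n) + 19·P(no stop). This returns every printed φ* and E[N]. The recursion adds one patient at a time with the outcome already known.

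**2. Same calculation for 20 patients.** P(X ≥ 8 | 20, 0.20) = 0.0321 exceeds 0.02143 and P(X ≥ 9) = 0.00998 does not, so b_20 = 9. Crossing probabilities are 0.0484, 0.2326, 0.5517 and 0.8342; E[N] is 19.47, 17.70, 14.47 and 10.78.

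**3. Patients entering during one window.** 177/30.44 = 5.8 months. Times 0.83, 1.4 and 1.8 this gives about 4.8, 8.1 and 10.5 patients.

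**4. Mean enrolled at the halt, rule as written, boundary alone.** Simulation with K = 20, Poisson arrivals, the 6-week hold and 3,000 trials per cell (Monte Carlo error about 0.1 at the 50% rate). These figures do not depend on when in the window RLTs occur, because only completed windows count.

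| RLT rate | Instantaneous outcomes | 0.83/month | 1.4/month | 1.8/month |
|---|---|---|---|---|
| 20% | 19.5 | 19.7 | 19.8 | 19.9 |
| 30% | 17.7 | 18.7 | 19.2 | 19.5 |
| 40% | 14.5 | 16.8 | 18.1 | 18.8 |
| 50% | 10.8 | 14.5 | 16.5 | 17.6 |

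At 50%, the rule halts before patient 20 enters in about 70, 58 and 45% of trials, against a crossing probability of 83%. In the remaining crossings the stratum is already full.

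**5. Add the lead-in, treating suspension as a halt.** If RLTs appear within the observation periods, the lead-in fires with probability P(≥2 of 3) + P(1 of 3) × P(≥1 of the next 3). At 50% this is 0.5 + 0.375 × 0.875 = 0.83; at 40% it is 0.352 + 0.432 × 0.784 = 0.69. RLT timing now matters and is assumed. Mean enrolled at a 50% rate, rule as written against RLTs counted as they occur among the first n treated, at 0.83, 1.4 and 1.8 per month:
- RLTs uniform over the window: 10.8 against 10.1; 12.5 against 11.5; 13.5 against 12.3.
- RLTs in the first 6 weeks: 6.5 against 6.2; 6.6 against 6.2; 6.6 against 6.2.

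The saving is about 0.3 to 1.2 patients at 50%, 0.2 to 0.7 at 40% and 0.1 to 0.3 at 30%.

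**6. Trials with no RLT seen at the 6-week hold** (50% rate, 1.4 per month). The written rule halts before full accrual in about 48% (uniform) or 18% (first 6 weeks). Counting RLTs as they occur gives about 62% and 52%.

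**7. Effect on the crossing probability.** Let R_n(t) be the RLTs known at time t among the first n treated. R_n(t) cannot fall, so R_n(t) ≥ b_n implies that the completed count also reaches b_n. The same trials cross, only sooner. In the simulations the revised rule never halted later and the crossing probabilities were identical.

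**The case against.** The strongest reply is that the lead-in acts first, and most often at exactly the rates where the boundary is slow. Step 5 bears this out: averaged over all trials, the saving is about one patient or less. This stands and sets the size of the point. It is qualified because a lead-in suspension leads to a decision and accrual may resume, and because a stratum that passes the lead-in has only the boundary left as a numeric rule (step 6).

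A reader might infer that known RLTs are ignored. The documents do not support that. Section 10.3 requires weekly review of all adverse events and continuous monitoring of all patients, and the DSMC discusses serious events every six weeks. These have no threshold, but they do see the events.

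A reader might also infer that the table is miscalculated or that E[N] is far too low throughout. Every entry reproduces. N can fairly be read as patients evaluated, and the boundary-alone gap is negligible at 20% and modest at 30%. For 19 patients with the lead-in included, mean enrolment falls below the printed E[N] at both those rates.

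Finally, 25 weeks is inferred from Section 6.3. A shorter follow-up would shrink the gap: with a 12-week window at 0.83 per month, the 50% figure falls from about 14.5 to 12.7. That is a further reason to define the term.

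**Conclusion.** The point holds as a should-fix for stratum C; strata A and B have their 19 and 10 patients (Section 5.1.5). As worded, the boundary leaves out RLTs in patients still inside an undefined follow-up period. E[N] and φ*, read as enrolment and as halting before full accrual, assume instantaneous outcomes. Boundary alone, the excess over E[N] is about 3.7 to 6.8 patients at a 50% RLT rate (14.5 − 10.8 to 17.6 − 10.8) and 2.3 to 4.3 at 40% (16.8 − 14.5 to 18.8 − 14.5). With the lead-in, the benefit of changing the rule averages 0.3 to 1.2 patients at 50%, and its main value is in trials that pass the lead-in. These figures assume a 177-day window, accrual of 0.83 to 1.8 per month and, for steps 5 and 6, the stated RLT timing. A stronger verdict, that the trial lacks effective safety stopping, is not supported.

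**What to change.** 1. Define full follow-up in 10.3, and reconcile the RLT window in 6.3 with the open-ended definition in 10.3.
2. Reword the trigger. Order patients by first dose and halt accrual as soon as the RLTs among the first n treated patients reach b_n for any n, whether or not those n have completed follow-up. Keep the same 0.02143 boundary, with b_20 = 9.
3. Print the 20-patient table. Its crossing probability at a 20% rate is 0.0484, slightly above the 0.0475 quoted for 19.
4. Label E[N] and φ* as assuming instantaneous outcomes, or give expected enrolment at the planned accrual rate.

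One tempting variant should be avoided: adding each RLT patient to n at once while RLT-free patients wait out the window. For 19 patients at the acceptable 20% rate, boundary alone, it raised the chance of halting before patient 19 to 0.09 to 0.34 in simulation, so b_n would have to be recalibrated. The first-n rule avoids this.

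The cost is a few sentences and one re-run table, with no extra patients. The crossing probability does not rise, provided that an RLT once counted is not reclassified and that treated patients are eventually evaluable.
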